 - c. SPMS, PPMS, or PRMS (progressive relapsing MS) phenotype, according to Lublin and Reingold criteria (19).
 - d. EDSS 2.0-6.0, inclusive.
 - e. Able to understand the consent process.
2. Exclusion criteria:
 - a. Known intolerance of ACTH or corticosteroids.
 - b. Diabetes mellitus, defined as pre-existing diagnosis, fasting blood glucose > 125 mg/dl, or glycosylated hemoglobin $\geq 6.5\%$, or 2-hour blood glucose > 200 mg/dl in an oral glucose tolerance test.
 - c. Osteoporosis, defined as pre-existing diagnosis or T-score on dual-energy X-ray absorptiometry (DEXA) scan of ≤ -2.5 in any of the following regions: left femoral neck, left total hip, right femoral neck, right total hip, L1-L4 (combined score).
 - d. Current serious medical condition which may interfere with subject's ability to complete the study, or for which pulsed ACTH therapy is contraindicated or might complicate current therapy (e.g. cancer, severe psychiatric illness, chronic infections, autoimmune disorders).
 - e. Treatment with cytotoxic broad-spectrum immunosuppressive agents (including but not necessarily limited to mitoxantrone, cyclophosphamide, alemtuzumab, or cladribine) within 3 years prior to randomization or during study participation.
 - f. Treatment with non-cytotoxic broad-spectrum immunosuppressive agents (including but not necessarily limited to corticosteroids, ACTH, azathioprine, mycophenolate mofetil, or methotrexate) within 3 months prior to randomization or during study participation.
 - g. Treatment with FDA-approved MS disease-modifying therapies (β -interferon, glatiramer acetate, fingolimod, teriflunomide, dimethyl fumarate, daclizumab or ocrelizumab) will be permitted. Treatment with these medications should be ongoing and stable for at least 3 months prior to randomization. Starting, stopping, or changing MS disease-modifying medications during the study is discouraged.
 - h. Treatment with natalizumab will be permitted, as long as treatment has been ongoing and stable for at least 3 months prior to randomization and JC virus antibodies are negative. Subjects taking natalizumab should be tested for JC virus antibodies every 6 months during the study (per standard of care), and if JC virus antibodies become positive, then the subject must either discontinue natalizumab or withdraw from the study.
 - i. Treatment with rituximab will be permitted, as long as treatment has been ongoing and stable for at least 3 months prior to randomization.

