2. Extrapolated to a 3 year follow up period, 60% of progressive MS patients will show a 20% or greater increase in T25FW.

Utilizing a significance level of 0.05 and equal sample sizes, 42 subjects per treatment arm would provide 80% power to detect a 50% difference in the proportion of subjects reaching the threshold of 20% worsening in T25FW ($P1 = 0.6$, $P2 = 0.3$, $\alpha = 0.05$, $\beta = 0.2$, 2-sided test). Given the length of the study, we anticipate a dropout rate of up to 10-20% of randomized subjects. To account for this possibility, a total sample size of 100 subjects (50 per treatment arm) will be randomized.

C. Randomization

The study will utilize blocked randomization stratified by study center, with equal (1:1) allocation to the ACTH and control groups.

D. Blinding

Study subjects, their referring physicians, the study monitor, and all study personnel who come in contact with study subjects (including site principal investigators, examining neurologists, study coordinators, nurses, and other study staff and their designated backups) will be blinded to treatment allocation. One investigator who will not come in direct contact with study subjects ([name]) as well as the study statistician and other members of the Data Safety Monitoring Board (DSMB, see section 7F) will be unblinded, to allow for assessment of any safety concerns that may arise over the course of the study.

E. Data Analysis Plan

Descriptive analyses of baseline characteristics and all outcome measures (primary and secondary) will include means with standard deviations or medians with ranges for continuous variables depending on the parametric or non-parametric distribution of the variables, and frequencies with percentages for categorical variables. Between group (ACTH and placebo) comparisons of baseline characteristics and baseline outcome measures will be done using two sample t-tests or Wilcoxon rank sum tests for parametric and non-parametric continuous variables, respectively, and Chi-square tests or Fisher's exact tests for categorical variables.

Models will adjust for age, gender, and MS phenotype; EDSS and disease duration will be included as covariates if significant in preliminary models. Interactions between treatment group and MS phenotype will be tested in each model; if significant, treatment effect will be evaluated in models stratified by MS phenotype.

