The possibility of mid-study therapy regimen change for some subjects (see Exclusion criteria g. and h.) will be accounted for in analysis by running models with and without these subjects to explore the impact of these changes on analysis results. If results from the two models are consistent, all subjects will be included in the final model.

There are multiple distinct outcomes of interest in this study; since each outcome measures a unique aspect of MS progression no adjustment for multiple comparisons is planned.

Primary endpoint:

Between group differences in the odds of a 20% or greater increase in T25FW, the primary outcome measure of clinical progression of MS, will be tested at 36 months using multiple logistic regression models adjusted for covariates. Generalized

estimating equation (GEE) models will be used to test for between group differences in change over time in clinical progression (20% or greater increase in T25FW) adjusted for covariates. To test for between group differences in time to clinical progression distribution curves, Cox proportional hazards models (conditional on model assumptions being met) or Kaplan-Meier analysis will be used.

Secondary endpoints:

Safety and tolerability

To evaluate safety and tolerability of ACTH, lists and descriptive statistics of adverse events, serious adverse event, and treatment compliance will be compiled and calculated for each group at each visit. Fisher's exact tests will be used to test for between group differences in specific adverse event rates, serious adverse event rates, and treatment compliance rates.

Between group differences in mean changes in physical exam and laboratory measures (weight, blood pressure, HgbA1c, bone mineral density) will be tested using two-sample t-tests. In addition, between group differences in the proportion of subjects with abnormal blood pressure, HgbA1C, electrolyte and bone mineral density levels will be tested using Chi-square tests or Fisher's exact tests.

Change in ambulation, cognition, and global measures of MS-related disability scores

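### Section 6.E moves the treatment effect into phenotype-stratified models when the phenotype interaction is significant, without saying that the overall effect stays the primary result; on plausible assumptions the false-positive rate rises from 5% to about 8-9%

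*Combined protocol and SAP*

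**What the plan says.** Section 4, inclusion criterion 1c, admits three groups: "SPMS, PPMS, or PRMS (progressive relapsing MS) phenotype". The expected mix is not given.

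Section 6.E adjusts all models for age, gender and phenotype and tests the treatment-by-phenotype interaction in each of them; "if significant, treatment effect will be evaluated in models stratified by MS phenotype". No significance threshold is given for the interaction. The plan does not say whether the overall estimate is still the primary result once the stratified models are run, or what pattern across phenotypes would count as success. On multiplicity, 6.E says that "no adjustment for multiple comparisons is planned", because each outcome captures a different aspect of progression.

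Under its primary-endpoint heading, 6.E tests the odds of a 20% worsening in T25FW at 36 months by covariate-adjusted logistic regression. Section 6.B sizes that overall comparison only: "42 subjects per treatment arm would provide 80% power", for 60% v 30% at two-sided 0.05. Section 6.C specifies "blocked randomization stratified by study center, with equal (1:1) allocation to the ACTH and control groups", so phenotype is not a stratification factor.

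**The concern.** Choosing covariates changes how one treatment effect is estimated. This rule is different: it changes which treatment effect is evaluated, and the trial's own data make the choice. When the interaction is significant by chance, the phenotype estimates have diverged by chance, and one of them is then likely to look significant too. The reason given for not adjusting concerns different outcomes; it does not cover testing one outcome in up to three phenotypes.

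At stake is the primary conclusion. The trial could report benefit or harm in one phenotype although ACTH has no effect in any of them. Readers could also be left unsure whether the headline is the overall comparison, which was sized, or a subgroup odds ratio, which was not.

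**Working it through.** **1. The plan's own figure.** With P1 = 0.6, P2 = 0.3, mean 0.45 and two-sided alpha 0.05:

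n = [1.96·√(2·0.45·0.55) + 0.842·√(0.6·0.4 + 0.3·0.7)]² / 0.3² = (1.379 + 0.565)² / 0.09 ≈ 42 per arm.

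The figure reproduces, with power 80.03%. It applies to the overall comparison.

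**2. Assumptions the documents do not supply.** (a) Interaction tested at 0.05, with 0.10 as a sensitivity case. (b) Each phenotype tested at two-sided 0.05. (c) Any one significant phenotype counts as a positive primary result. (d) The phenotype mix, which is varied.

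**3. Large-sample error under no effect.** Let z_i be the phenotype-specific statistic and f_i the phenotype's share. The overall statistic is Z = Σ√f_i·z_i, and the interaction statistic is Q = Σz_i² − Z² on k − 1 degrees of freedom. Under the null, Z and Q are independent, so

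error = 0.95 × 0.05 + 0.05 × P(some phenotype significant | interaction significant).

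The conditional probability comes from simulation (2,000,000 runs per mix):

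| Assumed mix | Conditional probability | Total error |
|---|---|---|
| 60/40 | 0.656 | 0.0475 + 0.0328 = 8.0% |
| 90/10 | 0.783 | 0.0475 + 0.0392 = 8.7% |
| 55/35/10 | 0.869 | 0.0475 + 0.0435 = 9.1% |
| 45/45/10 | 0.869 | 0.0475 + 0.0435 = 9.1% |

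The overall test alone gives 5.0%. Counting false benefit only, the rate goes from 2.5% to 4.1% (60/40) and 4.7% (45/45/10).

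**4. Replaced or added.** With two phenotypes, if both tests are significant then Σz_i² = Q + Z² > 3.84 + 3.84 = 7.68. At least one z_i² must then exceed 3.84, so a phenotype is significant as well. Keeping the overall test alongside the stratified ones therefore adds nothing to the total. With three phenotypes the simulated totals agree to within 0.01 percentage point.

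**5. Interaction tested at 0.10.** Large-sample totals are 9.4-9.8% with two phenotypes and 11.4-11.8% with three.

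**6. Trial-sized logistic models** (84 or 100 subjects, treatment and phenotype only, interaction at 0.05):
- Two phenotypes: 8.0-8.8% (Wald), 8.5-10.1% (likelihood ratio).
- Three about equal phenotypes: 8.5-9.4% (Wald), 10.2-11.4% (likelihood ratio).
- A third phenotype of 8-10 subjects: 6.7-7.4% (Wald), 11.9-13.3% (likelihood ratio).

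In these runs the overall test alone rejects in 5.2-6.3%, so part of the excess over 5% is ordinary small-sample error. One case combined a small third phenotype with a 0.10 threshold; it gave 8.0% (Wald) and 15.8% (likelihood ratio).

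**7. Estimability of a small PRMS group.** Let s be the PRMS share and take 42 per arm. An arm with event rate p has an empty cell with probability

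e(p) = (1 − sp)^42 + (1 − s(1 − p))^42 − (1 − s)^42,

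and the 2×2 table has one with probability 1 − [1 − e(0.6)]·[1 − e(0.3)].
- s = 5% (about 2 per arm): 1 − 0.410 × 0.362 = 85%.
- s = 10% (about 4 per arm): 1 − 0.758 × 0.686 = 48%.
- s = 15% (about 6 per arm): 1 − 0.908 × 0.847 = 23%.

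With 60% in both arms the figures are 83%, 43% and 18%.

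**8. Power to detect real heterogeneity.** Assume a 60/40 split, 60% v 30% in the larger phenotype and 60% v 60% in the smaller. The log odds ratios differ by 0.405 + 0.847 = 1.253. The variance is 1/(25.2·0.24) + 1/(25.2·0.21) + 2/(16.8·0.24) = 0.850, so z = 1.253/0.922 = 1.36 and power is Φ(1.36 − 1.96) ≈ 27%.

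**The case against.** The strongest reply is that the plan never says the overall result is dropped. The primary-endpoint text prescribes the 36-month test without condition, and following a significant interaction with stratified models is common practice. If those models only explain the overall result, the error stays at about 5%. A reader might infer that a significant interaction abolishes the overall answer; the text does not support that. The opposite reading is not written down either, and by step 4 the inflation does not depend on which reading is right. It depends on whether a significant phenotype may count as a positive result, and the plan is silent on that.

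It is also fair that the only stated 0.05 sits in the sample-size paragraph. The 8-9% is therefore conditional on unstated rules, and with a small third phenotype it moves outside that band in either direction.

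The trial is phase II, its stated main objective is safety and tolerability, and it openly declines multiplicity adjustment. That lowers the severity. It does not settle which result is primary for the one efficacy endpoint that was sized.

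Two further inferences should be resisted. PRMS is not inestimable as a rule: an empty cell occurs in most trials only at the 5% share among those tried. And the lack of stratification by phenotype does not cause the inflation; it only leaves the arm counts within a small phenotype to chance.

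**Conclusion.** The concern holds as an unprotected, data-dependent rule whose place in the primary conclusion is undefined. If the interaction and each phenotype are tested at two-sided 0.05 and any significant phenotype counts as positive, the false-positive rate for the primary endpoint is about 8-9% in large samples instead of 5%. It is roughly 7-13% when either a small phenotype or a 0.10 interaction threshold is allowed for, and higher in one case that combined the two. Every scenario tried exceeded the overall test alone. These figures illustrate what the wording permits. They are not a fixed property of the plan, because the threshold, the mix and the success rule are not in the documents. The matter should be fixed, but it does not undermine the design.

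**What to change.** In 6.E, state that the overall phenotype-adjusted treatment effect is the primary result for each endpoint whatever the interaction p-value, and that phenotype-specific estimates with 95% confidence intervals are descriptive only. With that rule the large-sample error returns to 5.0%. A Bonferroni correction across phenotypes within the stratified branch alone would not do this; it leaves about 6.9-7.3%.

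Pooling PRMS with another phenotype, or limiting the interaction test to the primary endpoint, is a matter of preference and is not needed to remove the problem.

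The change is to wording only, with no effect on design, sample size or data collection. The downside is that a phenotype-specific effect becomes hypothesis-generating, which is about all that 27% interaction power could support in the example above. Since 7.G schedules annual efficacy analyses, the wording is best settled before unblinded efficacy results are examined.

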Subjects will be asked to contact their study site if they develop new symptoms that are concerning to them. The local study coordinator will record the reported symptoms on the Unsolicited AE Form, which will be reviewed by the local investigator. An unscheduled study visit will occur if the local investigator deems these AEs as potentially serious, possibly related to study medication, and/or requiring in-person assessment. If the reported symptoms are interpreted as mild and/or unrelated to study medication, the subject may be referred to their primary physician or advised to report back by phone with updates about symptom

evolution/resolution. Unscheduled visits will not be routinely performed for suspected MS relapse (see section 7D, Relapses), although they may occur in this situation if the reported symptoms are interpreted as a possible treatment-related AE. Assessments/procedures performed at an unscheduled visit will include all of the assessments done at Visit 3 (see Table 1) with the exception of study drug distribution; any further assessments and/or procedures (e.g. physical examination, other tests, referrals) will be done at the discretion of the local investigator.

F. Early Termination and Intent to Treat

Once subjects are randomized, regardless of if or the length of time they have been on blinded treatment, they will be included in the efficacy (intent to treat) analysis if efficacy data are available (that is, if they have completed at least one annual follow-up visit). Subjects who withdraw (e.g., due to side effects) prior to completing the Month 12 visit will be asked to return the study drug to the site, and to participate in annual phone calls (Months 12 and 24), and to return to the site for the final visit at Month 36. Subjects who withdraw after completing the Month 12 visit will be asked to return the study drug to the site, and to complete the remaining annual study visits (i.e., Month 24 and Month 36) even though they are not receiving drug. Subjects are of course allowed to decline further participation, in which case they would be considered lost-to-follow-up.

G. Data Safety Monitoring

A DSMB will be formed and will consist of one MS specialist, one neurologist familiar with the evaluation and treatment of MS but not otherwise associated with the study, and the study biostatistician. A DSMB chairperson will be chosen from one of the two neurologists on the DMSB.

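### Section 6.E does not fix whether subjects who change MS therapy stay in the final model: 'consistent' is undefined, the inconsistent case has no rule, and the primary model is not exempt

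*Combined protocol and SAP*

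**What the plan says.** Section 6.E (Data Analysis Plan) addresses background-therapy changes in two sentences. The first reads: "The possibility of mid-study therapy regimen change for some subjects (see Exclusion criteria g. and h.) will be accounted for in analysis", and continues "by running models with and without these subjects to explore the impact of these changes on analysis results". The second is the condition: "If results from the two models are consistent, all subjects will be included in the final model".

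Both stand before the Primary endpoint heading and speak of models in general. The primary comparison is itself such a model. It "will be tested at 36 months using multiple logistic regression models adjusted for covariates", and the covariate rule is "Models will adjust for age, gender, and MS phenotype", with EDSS and disease duration added if significant in preliminary models.

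Therapy changes can happen. Criterion 4.2.g discourages starting, stopping or changing disease-modifying drugs but does not forbid it. Criterion 4.2.h can lead to natalizumab being stopped during the study. Neither gives an expected frequency.

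Section 7.F (Early Termination and Intent to Treat) says of randomised subjects, "regardless of if or the length of time they have been on blinded treatment", that "they will be included in the efficacy (intent to treat) analysis if efficacy data are available", meaning at least one completed annual visit. It does not mention a change in MS therapy and does not refer to 6.E.

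**The concern.** A sensitivity analysis normally sits beside a fixed main analysis. Here the comparison of the two fits feeds back into which subjects make up the final model. Three things are missing: what counts as consistent (direction, size of the estimate, p-value or interval), what happens if the results are not consistent, and any statement that the primary model stands outside the rule.

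Therapy change occurs after randomisation. Removing changers from the primary model would therefore give up part of the randomised comparison, and doing so after seeing both results would make the analysis set depend on the outcome. At stake is either the false-positive rate or the power of the primary test, depending on how the gap is filled.

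**Working it through.** **Inputs.** From section 6.B: 60% v 30%, two-sided 0.05, 80% power, 42 per arm, 50 per arm randomised, and "we anticipate a dropout rate of up to 10-20% of randomized subjects". Evaluable arm sizes are then 50 (no dropout), 45 (50 × 0.90), 42 (planned) and 40 (50 × 0.80). The share f of subjects who change therapy is an assumption, because the documents give none; 5, 10, 20 and 30% are shown, with change random and equal by arm.

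**1. The plan's own figure.** With pooled proportion 0.45,

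n = [1.960·√(2·0.45·0.55) + 0.842·√(0.24 + 0.21)]² / 0.30² = [1.379 + 0.565]² / 0.09 ≈ 42 per arm.

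The stated 42 reproduces, with power 80.0%.

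**2. Harm (a): the more favourable model may be chosen.** With no true effect and random change, the test statistics with and without changers are approximately bivariate normal with correlation √(1 − f). The chance that at least one exceeds 1.960 in absolute value is:

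| f | 5% | 10% | 20% | 30% |
|---|---|---|---|---|
| either model significant | 6.0% | 6.5% | 7.1% | 7.6% |

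A simulation of the logistic model adjusted for age, gender and phenotype (60% in both arms, 42-50 per arm, 20,000 trials per setting) gives 6.0-6.5, 6.6-6.9, 7.2-7.7 and 7.9-8.2%. The fixed all-subjects model rejects in 4.9-5.5% and the reduced model alone in 5.0-5.4%. The inflation therefore comes from the choice, not from the exclusion.

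**3. Harm (b): changers are always dropped.** Power = Φ{[0.30·√(n(1 − f)) − 1.960·√0.495] / √0.45}. For n = 42 and f = 10%, n(1 − f) = 37.8 and power is 75.6%.

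| per arm | all | f = 5% | 10% | 20% | 30% |
|---|---|---|---|---|---|
| 40 | 78.0 | 75.8 | 73.5 | 68.2 | 62.2 |
| 42 | 80.0 | 77.9 | 75.6 | 70.4 | 64.4 |
| 45 | 82.8 | 80.7 | 78.5 | 73.5 | 67.5 |
| 50 | 86.6 | 84.8 | 82.8 | 78.0 | 72.2 |

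Simulating the unadjusted two-proportion test over the same arm sizes gives about 76-85% at f = 5% and 63-73% at f = 30%, against about 80-88% with all subjects. The small differences from the table reflect the discreteness of the test.

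**4. A milder reading.** Suppose inconsistent means that the ratio of the two odds ratios falls outside 1/1.2 to 1.2, and the reduced model becomes final only then. At 10% change, power falls by about 1-2 points and type I error is 5.2-5.8%. This result is for 10% change and should not be carried to higher rates.

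**5. How often the missing branch would matter.** Under the planned effect, at 42-50 per arm, the two models fall on opposite sides of p = 0.05 in about 4.5-6% of trials at 5% change, rising to 19-21% at 30%. At 10% change the figure is 7-9%. The 1/1.2 to 1.2 rule would call 24-29% of those same trials inconsistent. The frequency depends heavily on the criterion that the plan leaves out.

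**6. The two harms exclude each other.** At 42 per arm with 10% change, an unadjusted Wald test has power 0.80 with all subjects, 0.75 without changers, and 0.82 if either may be used. Free choice raises type I error and also raises power. Always dropping changers costs power and leaves type I error near 5%.

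**The case against.** The text says 'if', not 'only if', and its first sentence gives an exploratory purpose. Reporting both models would fit it. This stands: a reader might infer that the plan commits to dropping changers when results differ, and the documents do not say so. But a condition on entry to the final model has no function unless the other case can lead elsewhere, and that case is left blank.

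Section 7.F can be read as supplying the default set, since its only condition is available efficacy data. That is a fair reading and makes the choice less open. But 7.F is framed around time on blinded treatment, does not mention therapy change and does not override 6.E. The two sections need reconciling.

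A reader might also infer serious bias because change may follow worsening and could differ by arm. If, as a pure assumption, 30% of placebo and 10% of ACTH subjects who worsen were to change therapy, the reduced model's type I error would be 8.5% at 42 per arm. Nothing in the documents suggests such a difference, so the conclusion does not rest on it.

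Finally, this is a phase II trial whose main objective is safety, and the effects at low change rates are modest. That is right, and it limits the weight of the point.

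**Conclusion.** The gap is real and should be fixed, but it is a gap in pre-specification and not a fatal flaw. As written, the subjects in the primary month-36 model can be settled after both results are known.

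The size is one of two alternatives: type I error of about 6-8% instead of about 5% if the better result may be chosen, or the power losses shown above if changers are always dropped. Adding the two together would be wrong. The power figures for always dropping changers are an extreme, and power can stay above 80% when few subjects change or dropout is low.

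All sizes rest on assumed change rates of 5-30%, with change unrelated to arm or outcome. The adjusted simulations use one phenotype indicator, take covariates as unrelated to outcome, and omit the conditional EDSS and disease-duration terms. The finding that the rule is incomplete rests on the text alone.

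**What to change.** Replace the conditional sentence in section 6.E with:

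> No subject is excluded from the primary model, or from any secondary model, on the basis of a change in MS therapy. Subjects are analysed as randomised in the section 7.F set, subject to the endpoint-specific data-quality rules (for example OCT). The model without subjects who changed therapy is a sensitivity analysis only and does not replace it.

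The reference to data-quality rules is needed because section 5.G lets subjects be left out of the OCT portion and drops scans below the minimum quality score.

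Optionally, extend the sensitivity analysis to changes in rituximab (criterion 4.2.i) and in dalfampridine or 4-aminopyridine (criterion 4.2.j). The present cross-reference covers only criteria g and h, while section 4.3.b itself warns that aminopyridine changes could confound the ambulation measures.

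The cost is a short change of wording and, if wanted, a somewhat wider sensitivity run. No extra subjects or data are needed: Table 1 has concomitant medications recorded at every visit from baseline. The small downside is that the primary estimate will include any effect of changed background therapy. Subjects in the 7.F set without a month-36 walk need a separate rule, which this wording does not settle.

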Walking impairment is a signature characteristic of MS, and of progressive MS in particular. Estimates of the prevalence of gait impairment in MS range from approximately 40-80%, and MS patients rate walking difficulties as one of the most burdensome aspects of the disease (20). Multiple walking assessment methods have been developed and evaluated in MS, including the gait-specific measures included in the present study: the 6MWT (21), the T25FW (22), the MSWS-12 (23) and the AI (24).

There is no clear "best" objective assessment of ambulation in MS. The most commonly used metrics are the EDSS (an overall measure of MS-related disability that is heavily "weighted" toward walking ability) and the T25FW. The T25FW is, as the name implies, a timed measurement of how fast a patient can safely walk 25 feet. Thus, it is primarily a measure of walking *speed*. In contrast, the 6MWT (a measure of the distance a subject can walk in 6 minutes) is a test of walking *endurance*. While impairments in walking speed certainly may cause problems in daily living for MS patients (e.g. crossing the street, getting to the bathroom on time), impairments in walking endurance probably account for the majority of walking-related functional limitations in MS. Several studies have evaluated and compared these metrics, and found both to be valid and reliable (25, 26). These studies found high correlations between walking speed and walking distance, but recommended a test of walking distance such as 6MWT be included in intervention studies where ambulatory function is an important outcome (as in the present study) (25). The 6MWT is more likely to capture the effect of motor fatigue on walking ability than is the T25FW, and is likely less susceptible to floor effects from subjects with no (or mild) gait impairment (27).

The literature contains much more data on T25FW than on 6MWT in MS patients. In particular, there is no published data on the change in 6MTW in MS patients over time. Therefore, change in the T25FW will serve as the primary endpoint of the study. Multiple studies have found that a change of 20% from baseline T25FW is both reliably detectable and clinically meaningful (28-31). **The primary endpoint of this study will be the proportion of subjects in each treatment arm who show a 20% increase in T25FW at the last study visit, compared to baseline.** Changes in 6MWT, MSWS-12, and AI will be secondary endpoints.

B. Safety and Tolerability

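### The primary T25FW endpoint is set at the last study visit in 5.A and at 36 months in 6.E, and the plan does not say which governs when the Month 36 value is missing

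*Combined protocol and SAP*

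**What the plan says.** Three statements in the combined protocol and SAP bear on this.

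- **5.A (Ambulation)** defines the primary endpoint as the proportion in each arm "who show a 20% increase in T25FW at the last study visit, compared to baseline".
- **6.E (Data Analysis Plan, Primary endpoint)** says the between-group difference "will be tested at 36 months using multiple logistic regression models adjusted for covariates". It adds that "estimating equation (GEE) models will be used to test for between group differences in change over time in clinical progression", and that time to progression will be analysed by Cox or Kaplan-Meier methods.
- **7.F (Early Termination and Intent to Treat)** says of randomised subjects that "they will be included in the efficacy (intent to treat) analysis if efficacy data are available", explained as "that is, if they have completed at least one annual follow-up visit".

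Section 7.F also tries to limit missing data. Those who withdraw before Month 12 are asked to "return to the site for the final visit at Month 36". Those who withdraw later are asked "to complete the remaining annual study visits (i.e., Month 24 and Month 36) even though they are not receiving drug". It accepts that some will not: "Subjects are of course allowed to decline further participation, in which case they would be considered lost-to-follow-up".

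Under 7.A and Table 1, T25FW is measured at baseline and Months 12, 24 and 36. Section 6.B expects up to 10-20% dropout and raises the sample from 42 to 50 per arm to allow for it.

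**The concern.** A subject last seen at Month 12 or 24 belongs to the 7.F analysis but has no Month 36 T25FW. Two scorings can be run from the text as it stands.

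- **Last visit (5.A with 7.F, read literally).** The Month 12 or 24 result is carried forward. Worsening accumulates with time, so this under-counts it, and more so in the arm that loses more subjects. That arm then looks better for a reason unrelated to treatment.
- **Month 36 only (6.E read alone).** The subject drops out of the primary test. Their earlier T25FW is discarded, numbers fall, and the comparison is biased if those lost would have worsened more or less often than those who stay.

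The choice should be fixed before results are known. Under 6.D the study statistician is unblinded, and under 7.G efficacy is analysed every year. These facts do not enlarge the missing-data effect. They do mean that a rule chosen late could be chosen, or appear to be chosen, with knowledge of results by arm.

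**Working it through.** All calculations are unadjusted; the planned test is covariate-adjusted.

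**1. The plan's own figure.** Inputs from 6.B: 0.60 vs 0.30, two-sided 0.05, power 80%. With mean proportion 0.45,

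n = [1.960·√(2·0.45·0.55) + 0.842·√(0.60·0.40 + 0.30·0.70)]² / 0.30² = 41.97, so 42 per arm. Power at 42 is 80.0%. The stated figure reproduces.

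**2. Worsening by visit (assumption: constant hazard to 60% at Month 36).** h = −ln(0.4)/3 = 0.305 per year. The cumulative proportion 1 − exp(−h·t) is 0.263, 0.457 and 0.600 at Months 12, 24 and 36. The Month 24 value is close to the 45% that 6.B takes from its source study.

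**3. Loss by visit (assumption: constant rate, total D by Month 36, none returning).** With r = (1−D)^(1/3):

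| | before M12: 1−r | last seen M12: r−r² | last seen M24: r²−r³ | seen at M36: r³ |
|---|---|---|---|---|
| D = 0.20 | 0.072 | 0.067 | 0.062 | 0.800 |
| D = 0.10 | 0.035 | 0.033 | 0.032 | 0.900 |

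The middle two columns are subjects in the 7.F analysis without Month 36. From unrounded terms they total 12.8% (6.4 of 50) at D = 0.20 and 6.5% (3.3 of 50) at D = 0.10.

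**4. Last-visit scoring, no true effect, loss 20% vs 10%.** Section 6.B gives no split by arm, so this split is an assumption. Leavers are first taken to worsen at the average rate, and those lost before Month 12 are excluded as in 7.F.

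- D = 0.20: (0.067·0.263 + 0.062·0.457 + 0.800·0.600)/0.928 = 0.566 (unrounded terms).
- D = 0.10: (0.033·0.263 + 0.032·0.457 + 0.900·0.600)/0.965 = 0.584.
- The false difference is 1.7 points, or 0.017·50 = 0.9 of a subject.
- Analysed n is 50·0.928 = 46.4 and 50·0.965 = 48.3. SE = √(0.566·0.434/46.4 + 0.584·0.416/48.3) = 0.102. The shift is 0.017/0.102 = 0.17 SE, so two-sided error = Φ(−1.96−0.17) + Φ(−1.96+0.17) = 5.3%.
- If half of all leavers return at Month 36: 0.584 vs 0.592, a difference of 0.8 points.
- If leavers would reach a proportion w by Month 36 other than 0.60 (leaver hazard −ln(1−w)/3, overall rate held at 0.60): w = 0.5 gives 1.1 points and 5.1% error; w = 0.8 gives 2.7 points and 5.8% error.

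**5. Month 36 only.** Power for 0.60 vs 0.30 is 78.0% with 40 per arm (20% loss) and 82.8% with 45 (10% loss). For bias under no true effect, the completer rate is (0.60 − D·w)/(1−D). With loss of 20% vs 10%:

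| w among those lost | D = 0.20 | D = 0.10 | false difference |
|---|---|---|---|
| 0.5 | 0.625 | 0.611 | −1.4 points |
| 0.6 | 0.600 | 0.600 | 0 |
| 0.7 | 0.575 | 0.589 | 1.4 points |
| 0.8 | 0.550 | 0.578 | 2.8 points |

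**6. Equal loss.** With the same D and w in both arms, both scorings give the same rate in each arm and so no false difference.

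**7. Imputation compared.** In a simulation with about 20% vs 10% loss and no true effect, Month-36-only scoring gave false differences of about 3 to 5 points when loss followed observed worsening. Last-visit scoring gave about 1 point when loss was unrelated to worsening. Imputation from Months 12 and 24 stayed within about 0.3 points, with power about 3 to 5 points above Month-36-only scoring. The size for Month-36-only scoring depends on how strongly loss is tied to worsening, so the ordering is firmer than the figures.

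**The case against.** The strongest reply is that 5.A and 7.F together already form a workable last-visit rule. That is fair, and it would be too strong to infer that the plan contains no rule at all. But 6.E names a different time point for the same test, and 7.F calls Month 36 the final visit, so the last study visit in 5.A may simply mean Month 36. The text does not decide between these readings.

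A reader might also infer that scoring only those with Month 36 contradicts 7.F. The documents do not support that. Section 7.F defines one population for all efficacy analyses, and a subject can contribute to the GEE and time-to-event models while having no value for the 36-month test. But 6.E does not offer those models as its way of handling a missing Month 36 result.

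Last-visit scoring is not wasteful: it uses the earlier visits, and its power is similar to that of imputation. At 20% loss it gives about 80.1-81.4%, assuming leavers split evenly between Months 12 and 24, control rates of 20-30% at Month 12 and 45% at Month 24, and half those rates on ACTH. Its weakness is the under-count, not lost precision. Month-36-only scoring is unbiased when leavers worsen at the average rate.

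The effect is small, needs unequal or outcome-related loss, and shrinks if subjects return as 7.F asks. All of that stands. So does the point that imputation is one of several defensible rules.

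**Conclusion.** The point holds as an unresolved inconsistency between 5.A, 6.E and 7.F about the primary test. Under the stated assumptions (constant worsening and loss rates, 20% vs 10% loss, no true effect, nobody returning), last-visit scoring produces a false 1.7 points with 5.3% error. The range is 1.1 to 2.7 points and 5.1% to 5.8% error for leavers reaching 50% to 80%. Month-36-only scoring gives −1.4 to 2.8 points over the same range, and 78.0% power at 20% loss in both arms.

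A reader might infer that the primary result could turn on the missing-data rule. With 24/40 vs 12/40 worsened among those observed and 10 missing per arm, p can run from below 0.001 to 0.69. Those ends require every missing subject in one arm to be counted as worsened and none in the other. Nothing in the documents suggests such a pattern. Nor is this a sample-size error, since 42 per arm reproduces exactly. It is a cheap improvement to the plan and does not threaten the trial's validity.

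**What to change.** In 5.A, replace the reference to the last study visit with Month 36, to agree with 6.E.

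In 6.E, state that for the primary logistic analysis of the 7.F population a missing Month 36 T25FW is multiply imputed, and that the 20% endpoint is derived from the imputed value. The imputation model should contain arm; baseline, Month 12 and Month 24 T25FW on a scale suited to its skew; EDSS; off-drug status; study centre (the stratifier in 6.C); and age, gender, MS phenotype and disease duration. Report Month-36-only and last-visit scoring as sensitivity analyses.

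The cost is wording and some programming, with no new visits or data. Imputation assumes that loss depends only on what was observed earlier (missing at random); the two sensitivity analyses probe that assumption without proving it. The change does not reach subjects lost before Month 12 who never return. They stay outside the 7.F population: 0.072·50 = 3.6 of 50 at 20% loss under the assumptions above.
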